6. STUDY POPULATION ANALYSES

6.1. Overview of Planned Analyses

The study population analyses will be based on the safety population, unless otherwise specified. All summary data and statistics are calculated from available data, unless otherwise specified.

Table 2 provides an overview of the planned study population analyses, with full details of data displays being presented in Appendix 14: List of Data Displays.

Table 2 Overview of Planned Study Population Analyses

Display Type	Data Displays Generated		
	Table	Figure	Listing
Disposition			
Retention Rate and Reasons for Withdrawals	Y		Y
Demography and Baseline Characteristics			
General Demographics Characteristics	Y		Y
Medical History and Concomitant Medications			
Medical History	Y		Y
Prior Medications	Y		Y
Concomitant Medications	Y		Y
Protocol Deviations			
Deviation of Inclusion/Exclusion Criteria	Y		Y
Important Protocol Deviations	Y		Y

NOTES:

- Y = Yes display generated.

6.1.1. Disposition

The reasons of screening failure will be summarized based on the screened population. The number and percentage of each reason will be tabulated.

A summary of subject disposition by phase will be provided, including the number and percentage of subjects entering oral/injection phase, the number and percentage of subjects completing oral/injection phase and the number and percentage of subjects withdrawing from oral/injection phase.

Subject disposition data will be presented in a listing.

6.1.2. Demographics

General demographics including age, self-identified gender when entering the study, and ethnicity will be summarized.

A subject's age is calculated using the year part of informed consent form (ICF) – year of birth collected in CRF.

6.1.3. Medical History

Summaries of medical history will be presented by GSK pre-specified body system categories as collected in the eCRF. Number and percentage of subjects in each category will be tabulated.

6.1.4. Prior and Concomitant Medications

Medications will be coded to therapeutic drug classes and generic drug names using the GSKDRUG 1.4 or later. Medications initiated prior to the Day 1 of the study will be counted as prior medications. Concomitant medications are defined as medications that are taken on or after the Day 1. Medications initiated prior to the Day 1 and continued after the Day 1 will be counted as both prior and concomitant medications.

Summaries showing the number and percentage of subjects who take prior or concomitant medications will be presented by therapeutic drug class and generic drug name.

6.1.5. Protocol Deviation

Important protocol deviations (PD) will be summarized PD category and subcategory, and will also be presented in a listing. A separate summary table and a listing will be provided for subjects with deviation of the inclusion/exclusion criteria in the safety population

7. PRIMARY STATISTICAL ANALYSES

7.1. Safety Analyses of CAB LA

Four study phases are defined for this study: screening phase, oral phase, injection phase and follow-up phase (see [Appendix 4](#) for the definition of each phase).

The primary safety analysis will be conducted after all ongoing participants complete the Week 41 visit and datasets have been authorized. All data from injected participants collected from Week 5 to Week 41 (i.e., in the injection phase) will be analysed. Analysis endpoints will include Grade 2 or higher clinical and laboratory events that occur from the initial injection to 8 weeks after the last injection among participants who receive at least one injection.

The extended safety analysis will be conducted after all ongoing participants complete the Week 89 visit and datasets have been authorized. All data from injected participants collected from Week 5 to Week 89 (i.e., in the injection phase and the follow-up phase) will be analysed. Analysis endpoints are the same as in the primary safety analysis.

To assess safety, the number and the percent of participants experiencing each safety endpoint will be tabulated. Each participant will contribute once in each category (i.e., only for the highest severity AE) for the evaluation of safety.

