10.3.1. Primary Analyses

10.3.1.1. Safety Analyses

All safety analyses will be performed on the Safety Population.

The primary safety analysis will include Grade 2 or higher clinical and laboratory events that occur from the initial injection to 8 weeks after the last injection among participants who receive at least one injection. In an extended safety analysis, all data from enrolled participants will be analyzed regardless of how many injections they receive.

To assess safety, the number and the percentage of participants experiencing each safety endpoint will be tabulated. Each participant will contribute once in each category (i.e., only for the highest severity AE for each participant) for the calculation of event rates.

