10.3.1.1.2. AEs

AEs will be tabulated using MedDRA preferred terms. The number and percentage of participants experiencing each specific AEs (All AEs, Grade 2 or higher, and SAEs) will be tabulated by severity and by relationship to study product. For the calculations in these tables, each participant's AEs will be counted once under the maximum severity or the strongest relationship to study product. AEs leading to withdrawal will also be summarized. AEs will be summarized for those that are treatment emergent during LA dosing separately from those that are treatment emergent during oral dosing and also for those that are treatment emergent across the entire treatment phase of the study (combining both LA and oral dosing).

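### SAP 7.1 narrows the protocol's extended safety analysis to injected men without declaring it, contradicts itself on whether late events count, and leaves out the combined oral and LA adverse event summary

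*SAP*

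**What the plan says.** **Protocol.** Section 10.3.1.1 sets the default: "All safety analyses will be performed on the Safety Population". The primary safety analysis counts Grade 2 or higher events "from the initial injection to 8 weeks after the last injection among participants who receive at least one injection". The wider analysis follows: "In an extended safety analysis, all data from enrolled participants will be analyzed regardless of how many injections they receive". Section 10.3.1.1.2 asks for adverse events to be summarised separately for oral and for LA dosing, and also "across the entire treatment phase of the study (combining both LA and oral dosing").

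**SAP.** Section 7.1 defines the primary endpoints as "Grade 2 or higher clinical and laboratory events that occur from the initial injection to 8 weeks after the last injection". For the extended analysis it names the data as "All data from injected participants collected from Week 5 to Week 89 (i.e., in the injection phase and the follow-up phase"), and adds: "Analysis endpoints are the same as in the primary safety analysis". The Section 4 table assigns both the primary and the extended LA analyses to the Safety Injection population, meaning men with at least one injection. The SAP synopsis mentions that population for the primary analysis only. Section 2.1, which lists changes from the protocol, covers adverse events of special interest and nothing else. Section 7.1.2 tabulates adverse events by study phase, with Safety-population men who entered the phase as denominator.

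**The concern.** Three things do not line up.

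- **Population.** The protocol's extended analysis is open to men with no injections. The SAP's version is not, and a reader of SAP 2.1 would not learn that anything had changed.
- **Timing.** The primary endpoints carry their own time limit. Reusing them unchanged for a Week 89 analysis brings that limit along, and it conflicts with the sentence that takes in follow-up data. Two programmers could produce different extended tables, each with SAP text to support them.
- **Combined summary.** The protocol promises adverse events over oral and LA treatment together. The SAP text, its treatment states and its list of displays do not specify this.

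At stake is a simple descriptive result: the share of treated men who had an event over their whole exposure, with each man counted once. Residual drug can persist for months after the last injection (Protocol 3.3.1), and adverse events are collected to the final follow-up visit (Protocol 9.2.1), so the extended analysis should say clearly what it counts.

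**Working it through.** The documents give no power calculation, event count or target precision on this point. The check sets the texts side by side and does the schedule arithmetic.

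**1. Population**

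| Source | Extended analysis covers |
|---|---|
| Protocol 10.3.1.1 | Enrolled men, any number of injections |
| SAP 7.1 | Injected men |
| SAP 4 | Safety Injection population |
| SAP 2.1 | No change declared |

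Planned numbers (Protocol 5.2): about 48 enter the oral phase and about 40 the injection phase. Oral-only men: 48 − 40 = 8, and 8/48 = 17%.

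**2. Timing**

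Let L be the date of a man's last injection.

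- Endpoint window (SAP 7.1): first injection to L + 8 weeks.
- Follow-up phase (SAP 10.4.1): dates later than L + 8 weeks.

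The two do not overlap, so no follow-up-phase event can meet the endpoint as defined. Yet the sentence just before says follow-up-phase data will be analysed.

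Schedule check for a man given all five injections: the last is at Week 33; 33 + 8 = Week 41 and 33 + 56 = Week 89, both matching the stated visits.

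- First injection to final visit: 89 − 5 = 84 weeks.
- Inside the endpoint window: 41 − 5 = 36 weeks.
- Follow-up: 89 − 41 = 48 weeks, and 48/84 = 57%.

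For a man who stops after one injection at Week 5, the window closes at Week 13 and follow-up ends at Week 5 + 56 = 61. Follow-up is then 48 of 56 weeks, or 86%.

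The two readings give different analyses:

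- If the 8-week limit governs, the Week 89 run has the same men, grade threshold and window as the Week 41 run, and adds nothing but data corrections.
- If the Week 89 sentence governs, it adds up to 48 weeks of Grade 2 or higher events per man, still without the oral-only men.

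**3. Combined oral and LA summary**

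- SAP 7.1.2 tabulates by phase with phase-specific denominators.
- The adverse event treatment states in SAP 10.4.2.1 contain no combined state.
- Tables 2.3 to 2.15 in Appendix 14 carry no combined title or programming note.

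The combined figure cannot be rebuilt from the phase columns. If *a* men have an event in the oral phase and *b* in the injection phase, the number with an event in either lies between max(*a*, *b*) and min(*a* + *b*, 48). Which value applies depends on how many men are in both counts, and the two columns have different denominators (about 48 and about 40).

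**The case against.** A reader might infer that the Week 89 analysis simply repeats the Week 41 one, or that late events and oral-only men drop out of the report. The documents do not support either reading.

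- **Not plainly a repeat.** The sentence before the endpoint statement takes in the follow-up phase. The author may well have used endpoints to mean the type of event, applied to the window just given. The text is self-contradictory, which is a smaller fault.
- **Late events are reported.** Adverse events and Grade 2 or higher laboratory events are tabulated by phase (SAP 7.1.2, 7.1.3). Tables 2.3 to 2.16 are on the Safety population and are due at both Week 41 and Week 89. Listings cover all adverse events.
- **Oral-only men are reported.** They leave the study when they stop oral dosing (Protocol 8.1, 8.2.1), so they have no later visits to omit. SAP 8.2 analyses their events to their last visit.
- **Table layouts cannot be seen.** Mock shells are available only on request, so a total column may exist. The 5% rule for common adverse events refers to the study as a whole, which implies some across-phase count.
- **Purpose of follow-up.** Protocol 3.3.1 lists the 56 weeks as mitigation for resistance after stopping CAB LA, and Protocol 9.5 uses the follow-up samples for terminal PK. Late adverse events are not given as the chief reason.
- **No hypothesis is tested**, so no inference turns on this.

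All of this stands, and it limits the size of the point. It does not supply the protocol's extended analysis, explain the undeclared change of population, or specify the combined summary. A total column that might exist in an unseen shell is not a planned analysis.

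**Conclusion.** The point holds as a set of three protocol-to-SAP discrepancies: an undeclared narrowing from enrolled to injected men, a self-contradictory endpoint window, and an unspecified combined oral and LA adverse event summary. No safety data are lost. The protocol's extended analysis and a subject-level combined estimate are what is missing, and phase percentages cannot stand in for them.

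On size, 57% is a share of scheduled weeks for a five-injection man and says nothing about the share of events. The 17% rests on approximate planned numbers, and men who leave the oral phase may be replaced. The protocol does not define enrolled; it is taken here to mean men who started oral CAB, which matches the Safety Population. The correction is worth making because it is nearly free, but nothing here puts the trial's conclusions at risk.

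**What to change.** 1. In SAP 7.1, replace the sentence that reuses the primary endpoints. State that the extended endpoint counts Grade 2 or higher clinical and laboratory events through the last follow-up visit (Week 89 for a man given all five injections).
2. Run the protocol's extended analysis on all data in the Safety population. Keep the injected-only Week 5 to 89 summary as a separate LA estimate, so that oral-phase events are not mixed into it. Alternatively, declare and justify the narrowing in SAP 2.1. Either way, make the synopsis and Section 4 agree on which population the extended analysis uses.
3. Add a column for the entire treatment phase (oral plus LA) to adverse event Tables 2.3 to 2.15, counting each man once over the Safety population. This column stops at the end of LA treatment, so it should not be merged with the extended analysis, which runs through follow-up.

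The cost is SAP wording, one extra column and some programming, with no new data collection.

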7.1.1. Injection Site Reaction

The number and percentage of participants experiencing each type of injection site reaction sign or symptom will be tabulated by severity from the safety injection population. For a given sign or symptom, each participant’s ISR will be counted once under the maximum severity for all injection visits. Overall summary of ISR and summary of ISR by needle length will both be provided. ISR related details, such as cardiovascular activity, strength training exercise, will be listed only.

[Table 3](#) provides an overview of the planned ISR analyses, with full details of data displays being presented in [Appendix 14](#): List of Data Displays.

Table 3 Overview of Planned ISR Analyses

Display Type	Data Displays Generated						
	Stats Analysis			Summary		Individual	
	T	F	L	T	F	F	L
ISR Analyses							
All ISR Symptoms				Y			Y

NOTES:

- T = Table, F = Figure, L = Listing, Y = Yes display generated.
- Stats Analysis = Represents TFL related to any formal statistical analyses (i.e. modelling) conducted.
- Summary = Represents TFL related to any summaries (i.e. descriptive statistics) of the observed raw data.
- Individual = Represents FL related to any displays of individual subject observed raw data.

7.1.2. Adverse Events

Adverse events will be tabulated using MedDRA (v20.0 or above) system organ class (SOC) and preferred terms (PT), or preferred terms alone, by study phase. The number and percentage of participants experiencing each specific AEs (Grade 2 or higher, All AEs, SAEs, AEs leading to permanent treatment discontinuation or study withdrawal) will be tabulated. Number of subjects in the safety population who entered the study phase will be used as denominator in the calculation of percentages.

Drug-related AEs, SAEs, and Grade 2-4 AEs will also be tabulated. Any AE is assumed to be study treatment-related if relationship is marked 'YES' on CRF or value is missing. In addition, a summary table will be created for AEs by maximum severity by study phase. Common AEs are defined as AEs occurring in $\geq 5\%$ subjects during the study (based on preferred term). Common AEs, common non-serious AEs, common Grade 2-4 AEs, and common drug-related Grade 2-4 AEs will be tabulated.

All AE tables will be presented in a decreasing frequency order of SOC or PT unless otherwise specified.

[Table 4](#) provides an overview of the planned AE analyses, with full details of data displays being presented in [Appendix 14](#): List of Data Displays.

Table 4 Overview of Planned AE Analyses

Display Type	Data Displays Generated						
	Stats Analysis			Summary		Individual	
	T	F	L	T	F	F	L
AE Analyses							
All AEs				Y			Y
Grade 2 or higher AEs				Y			Y
SAEs				Y			Y
AE leading to treatment discontinuation or study withdrawal				Y			Y
Drug-related AEs				Y			
Drug-related SAEs				Y			
Drug-related Grade 2 or higher AEs				Y			
Common AEs				Y			
Common non-serious AEs				Y			
Common Grade 2-4 AEs				Y			
Common drug-related Grade 2-4 AEs				Y			

NOTES:

- T = Table, F = Figure, L = Listing, Y = Yes display generated.
- Stats Analysis = Represents TFL related to any formal statistical analyses (i.e. modelling) conducted.
- Summary = Represents TFL related to any summaries (i.e. descriptive statistics) of the observed raw data.
- Individual = Represents FL related to any displays of individual subject observed raw data.

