		Day 1	Day 28 (Week 4)	Day 35 (Week 5) Injection 1	Day 42 (Week 6)	Week 9 Injection 2	Week 10	Week 17 Injection 3	Week 18	Week 25 Injection 4	Week 26	Week 33 Injection 5	Week 34	Week 37	Week 41	Week 53, 65, 77	Week 89	
TRUST for Syphilis screen	X																	
Plasma for CAB concentration ^{m,n,o}			X ^m	X	X	X	X	X	X	X	X	X	X	X	X	X	X	X
Plasma storage sample ^p	X	X	X	X	X	X	X	X	X	X	X	X	X	X	X	X	X	X

AE: Adverse events, BMI: Body mass index, CAB: Cabotegravir, CAB LA: Cabotegravir long-acting, ECG: Electrocardiogram, HbsAg: Hepatitis B surface antigen, HIV: Human Immunodeficiency Virus, HCV: Hepatitis C Virus, ISR: Injection site reactions, SAE: Serious adverse event, HIV-PrevTSQc: HIV-Prevention Treatment Satisfaction Questionnaire (change): TRUST: Tolidine Red Unheated Serum Test, RNA: Ribonucleic acid.

- Screening (including drug screen) is to be performed within 30 days of the first dose in the Oral Phase of the study. See [Appendix 2](#)
- Inclusion/exclusion criteria will be fully assessed at the Screening visit. Changes between the screening visit and the Day 1 visit should be assessed to ensure eligibility, including additional assessments performed at Day 1.
- A full physical exam will be performed at Week 89.
- Weight will be collected at Screening and at Week 89. Height and BMI will be collected at Screening only.
- Oral phase consists of 28 days with a 7 day washout period between Day 28 (last oral dose) and Day 35 (first injection visit).
- HIV-PrevTSQc: HIV-Prevention Treatment Satisfaction Questionnaire (change) will be given at Week 10 only (after 2nd injection).
- ISR AE 7 Day Post Injection Diary will be distributed at the injection visit at Week 5, 9, 17, 25 and 33 and returned to the clinic at weeks 6, 10, 18, 26, and 34. For participants having ISR on the last day of week 5, 9, 17, 25 and 33, additional ISR AE Weeks 2 – 12 Post Injection Diary will be distributed at weeks 6,10, 18, and 26,34. Participants will be asked to bring the diary to each clinic visit.
- Vital sign measurements will be performed following 5 minutes of rest.
- Qualitative HIV Nucleic Acid Amplification Testing (NAAT) will be performed at Screening. See [Appendix 9](#) for the HIV testing algorithm at screening, Day 1 and during the course of the study.

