- HIV PoC (Point of care) test will be performed at each time point during the course of the study and must be reviewed prior to IM dosing. See [Appendix 9](#) for the HIV testing algorithm at screening, Day 1 and during the course of the study.
- ECGs will be performed following 5 minutes of rest in a semi-supine position.
- Liver Chemistry Tests include Alanine aminotransferase (ALT), Aspartate aminotransferase (AST), Bilirubin total and direct.

- m. Oral Pharmacokinetic (PK) sampling at trough will be collected for all subjects prior to dose within 20 to 28 hours following oral administration the day prior. Intensive oral PK sampling will be collected from approximately 16 participants as shown in [Table 2](#).
- n. PK sampling for Injection phase: All PK samples will be collected prior to CAB LA injections at Week 5, 9, 17, 25, and 33 with the exception of 1-week post injection samples at Weeks 6, 10, 18, 26, 34, week 37(4-week post injection sample) and Week 41
- o. Long-term follow up PK samples: PK sampling during follow up will occur at, Week 53, 65, 77, and 89.
- p. Additional testing is required for participants who have a reactive or positive HIV test after enrolment. Stored plasma from the visit previous to the positive test should be tested for HIV using the 4th generation HIV test to best estimate time of infection. HIV acquisition must be confirmed by either western blot, HIV ½ Multispot or the Geenius HIV Confirmation ½ Assay, and HIV RNA.
- q. Visit may occur in a window ± 3 Days

Table 2 SCHEDULE OF INTENSIVE ORAL PK APPROXIMATELY 16 PARTICIPANTS) ^{a,b}

	Day 25	Day 26	Day 27							Day 28	
	Check-in	Oral dose administered (e.g. 8AM)	Prior to oral dose (e.g. 7:55AM)	Oral dose administered (e.g. 8AM)	1-hour post dose (e.g. 9AM)	2-hour post dose (e.g. 10AM)	3-hour post dose (e.g. 11AM)	4-hour post dose (e.g. 12AM)	8-hour post dose (e.g. 4PM)	24-hour post dose (e.g. 8AM)	Oral dose administered (e.g. after 8 AM)
Plasma for CAB concentration			X		X	X	X	X	X	X	

- a. PK sampling may occur ± 15 min
- b. Central lab tests for the intensive oral PK subjects refer to [Table 1](#).

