7.1.3. Clinical Laboratory Tests

All clinical laboratory tests will be graded according to the [Appendix 7](#) from the study protocol. Grade 2 or higher laboratory events will be tabulated by number and percentage of subjects with the event by study phase.

Change from baseline in hematology, fasting chemistry, fasting lipid profile, and coagulation profile will be summarized by visit. For the definition of baseline, refer to Section [10.5.2](#). Urinalysis and urine chemistry results will be summarized by visit as either categorical values or as continuous values, depending on the type of the parameter.

For each lab test, shift from baseline table will be provided based on toxicity grade, both by visit and for the shift to maximum toxicity grade in each study phase. Data collected at unscheduled visits will not be included in the by-visit summary, but will be used in the calculation of maximum grade in each study phase. Subjects having both high and low values will be counted in both High and Low categories for the summary by study phase.

All lab data, as well as lab data for subjects with Grade 2 or higher abnormalities, will be listed. Abnormal data will be listed with an indicator, which is low/high relative to normal range. All laboratory results from local labs, if any, will be listed only

[Table 5](#) provides an overview of the planned lab test analyses, with full details of data displays being presented in [Appendix 14](#): List of Data Displays.

Table 5 Overview of Planned Lab Test Analyses

Display Type	Absolute				Change from Baseline			
	Summary		Individual		Summary		Individual	
	T	F	F	L	T	F	F	L
Laboratory Test Analyses								
Grade 2 or high laboratory events	Y							
Clinical Chemistry				Y	Y			
Hematology				Y	Y			
Fasting Lipid Profile				Y	Y			
Coagulation Profile				Y	Y			
Urinalysis and Urine Chemistry	Y			Y	Y			
Other lab data including local lab				Y				

- T = Table, F = Figure, L = Listing, Y = Yes display generated.
- Stats Analysis = Represents TFL related to any formal statistical analyses (i.e. modelling) conducted.
- Summary = Represents TFL related to any summaries (i.e. descriptive statistics) of the observed raw data.
- Individual = Represents FL related to any displays of individual subject observed raw data.

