10.4. Appendix 4: Study Phase and State

10.4.1. Treatment Phases

Assessments and events will be classified according to the time of occurrence relative to the start date of study treatment.

Treatment Phase	Definition
Screening Phase	Date < Date of first Oral CAB
Oral Phase	Date of First Oral CAB <= Date <= Date of First CAB LA Injection -1 day; for subjects who discontinued before receiving CAB LA Injection, the end date of the oral phase is the date of last study visit.
Injection Phase	Date of First CAB LA Injection <= Date <= 8 weeks after Last CAB LA Injection
Follow-up Phase	Date > 8 weeks after Last CAB LA Injection

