10.6.2. Study Population

Demographics

Age

- As the month and date of birth will not be collected in the study, the age will be calculated as Year of ICF – Year of Birth;
- Birth date will be presented in listings as ‘YYYY’.

Body Mass Index (BMI)

- Calculated as Weight (kg) / [Height (m)²]

Extent of Exposure

- Duration of exposure to study drug will be calculated based on the formula:
 - The duration of exposure for oral phase is defined as the number of days starting from the first oral dose to the last oral dose.
 - Duration of exposure for injection phase is defined as the number of injections (1, 2, 3, 4 or 5)
 - Overall exposure to CAB is defined as number of days from the first oral dose to 8 weeks following the participant’s last injection. If a participant does not enter the injection phase, the overall CAB exposure for the study will be defined as the number of days from the first oral dose to the last oral dose.
 - Overall exposure to the study (for safety evaluation) is defined as number of days from the first dose to last visit (including unscheduled visit) in days.
- The cumulative dose will be based on the formula:
 - Cumulative dose in oral phase is defined as (number of tablets dispensed – number of tablets returned) * 30 mg

Extent of Exposure

- Cumulative dose in injection phase is defined as number of injections * 600 mg

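### Adverse-event percentages by study phase cannot be compared across phases that last about 5, 36 and 48 weeks, and the SAP defines no like-for-like person-time per phase

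*SAP*

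**What the plan says.** SAP 7.1.2 presents adverse events by system organ class and preferred term, or by "preferred terms alone, by study phase", and sets the denominator: "Number of subjects in the safety population who entered the study phase will be used as denominator in the calculation of percentages". SAP 7.1 counts each subject once per category, at the highest severity, so these are percentages ever affected during the phase. The display list in SAP 10.14.5 has no separate table set per phase and no exposure-adjusted rate.

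For laboratory data, SAP 7.1.3 says: "Grade 2 or higher laboratory events will be tabulated by number and percentage of subjects with the event by study phase". It also plans shifts to the maximum grade in each phase, and change from baseline and grade shifts by visit. It states no laboratory denominator.

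SAP 10.4.1 sets the phase boundaries. The oral phase is "Date of First Oral CAB <= Date <= Date of First CAB LA Injection -1 day". The injection phase runs from the first injection to 8 weeks after the last one, and follow-up is everything later. SAP 10.6.2 measures oral exposure in days, but for injections it states: "Duration of exposure for injection phase is defined as the number of injections (1, 2, 3, 4 or 5". Its overall exposure measures, in days, pool the phases.

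Protocol 10.3.1.1.2 asks for the split: "AEs will be summarized for those that are treatment emergent during LA dosing separately from those that are treatment emergent during oral dosing". SAP 10.5.1 lists oral CAB and CAB LA as ordered display groups 1 and 2.

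**The concern.** The chance of at least one event rises with the time a subject is watched, and the chance of at least one abnormal result rises with the number of samples. If the phases differ in both, their percentages differ even when the drug adds nothing in any phase.

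The trial is single-arm with about 40 injected men, so the oral and follow-up results are the only internal reference for the injection results. A reader who compares them could take a difference in observation time for a difference in risk. Early stopping adds a distortion inside the injection phase: someone who leaves after one injection contributes 8 weeks instead of 36 but has the same weight in the denominator.

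**Working it through.** **Phase lengths** (SAP 10.4.1 and the nominal visits in Protocol 2).
- Follow-up: 33 + 8 = 41, and 89 − 41 = 48 weeks. This reproduces the 48 weeks in Protocol 5.1. Likewise 89 − 33 = 56 reproduces the stated 56 weeks after the last injection.
- Injection: (33 + 8) − 5 = 36 weeks.
- Oral: Day 1 to Day 34, so 34 days or 34/7 = 4.9 weeks, taken as 5. It includes the "7 day washout period between Day 28 (last oral dose) and Day 35 (first injection visit". SAP 2.3 describes the oral lead-in as Day 1 to Week 4, but the date rule in 10.4.1 governs the tabulation.

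**Scheduled post-baseline draws** (Protocol Table 1; Day 1 is the baseline sample). Full haematology and chemistry fall at Day 28; at Weeks 5, 6, 9, 17, 25, 33 and 41; and at Week 89, which is 1, 7 and 1. Weeks 53, 65 and 77 have a reduced panel: "Liver Chemistry Tests include Alanine aminotransferase (ALT), Aspartate aminotransferase (AST), Bilirubin total and direct". Liver tests therefore number 1, 7 and 4.

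**Adverse events under equal risk.** The documents give no event rate, so the rates are assumed. P(at least one event) = 1 − exp(−rate × weeks).

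| Rate per 100 person-weeks | Oral, 5 wk | Injection, 36 wk | Follow-up, 48 wk |
|---|---|---|---|
| 0.5 | 2.5% | 16.5% | 21.3% |
| 1 | 4.9% | 30.2% | 38.1% |
| 2 | 9.5% | 51.3% | 61.7% |

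For the middle row: 1 − exp(−0.05) = 4.9%, 1 − exp(−0.36) = 30.2%, 1 − exp(−0.48) = 38.1%. Divided by person-time, every row gives the same rate in all three phases.

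**Early stopping.** At the same rate of 1, a subject with one injection has an 8-week injection phase and a chance of 1 − exp(−0.08) = 7.7%, against 30.2% for a completer.

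**Laboratory under equal per-draw risk** (assumed p; independent draws). P = 1 − (1 − p)^k.

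| p per draw | Full chemistry, k = 1/7/1 | Liver tests, k = 1/7/4 |
|---|---|---|
| 2% | 2.0 / 13.2 / 2.0% | 2.0 / 13.2 / 7.8% |
| 5% | 5.0 / 30.2 / 5.0% | 5.0 / 30.2 / 18.5% |
| 10% | 10.0 / 52.2 / 10.0% | 10.0 / 52.2 / 34.4% |

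Independence overstates the gap. With p = 5% and a beta-binomial model, the injection figure is about 20% at within-subject correlation 0.2 and about 12% at 0.5. If the Week 5 sample precedes the injection and is left out, six independent draws give 26.5%. A late Week 41 visit, which the ±3-day window allows, moves one draw to follow-up (6 and 2). None of these changes removes the gap.

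**The case against.** The strongest reply is that no one plans the comparison. SAP 2.4 rules out formal hypotheses, the primary safety analysis is confined to the injection phase (SAP 7.1), and oral safety is a separate secondary objective whose section (8.2) says openly that its time frame differs. For those objectives a percentage within the phase is a proper answer. That stands, and it limits the point to how the tables are read. It does not dispose of it, because the tables are organised by phase and nothing in them would show the reader how unequal the phases are.

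Three stronger readings are tempting and are not supported:
- *Nothing corrects the laboratory data.* SAP 7.1.3 already plans by-visit changes and shifts, which do not depend on the number of draws in a phase. Draws per week are also nearly equal in the oral and injection phases (1/5 = 0.20 and 7/36 = 0.19); there, duration is what differs. Adverse events have no by-visit equivalent.
- *A 0% for lipids, coagulation or urinalysis in the oral or follow-up phase would mean untested.* These have scheduled post-baseline samples only at Week 41, but the SAP states no laboratory denominator and its table shells are not shown, so how an untested analyte would print cannot be known. What can be said is that the denominator is missing.
- *CAB LA is bound to look several-fold worse, with recovery afterwards.* Under a constant rate, follow-up shows the highest adverse-event percentage, and the sizes rest on assumed rates. Follow-up is not drug-free either: Protocol 3.3.1 says CAB can persist for months.

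It is also fair that person-time can be derived from the SAP 10.4.1 dates. The SAP simply does not ask for it.

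**Conclusion.** The point holds as a matter of interpretation. The percentages within each phase, including the primary injection-phase results, are valid, and no planned inference is wrong. What fails is comparison across phases: identical risk would give roughly 5%, 30% and 38% at 1 event per 100 person-weeks, with the range shown for rates of 0.5 to 2. The ordering follows from phase length alone; the sizes rest on the assumed rates, a constant hazard, full-length phases and equal ascertainment. The laboratory version applies mainly to non-liver chemistry and haematology (1/7/1 draws), less to liver tests (1/7/4), and is partly offset by tables already planned. This is a worthwhile, inexpensive improvement, not a defect in the primary analysis.

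**What to change.** 1. In SAP 10.6.2, define time at risk in days for each phase. For the injection phase, use the first injection to the earlier of 8 weeks after the last injection or last contact.
2. Keep the planned percentages. Add exposure-adjusted rates per 100 person-weeks to the main by-phase adverse-event tables only: all events, Grade 2 or higher, and drug-related Grade 2 or higher. Say whether the numerator is all events or first events; if first events, stop a subject's time at the first one.
3. Leave injection site reactions out of those rates or show them separately. They cluster after dosing, so an average weekly rate describes them poorly.
4. For Table 2.16 and the maximum-grade shifts, use as denominator the subjects with at least one post-baseline result for that analyte in that phase. Print *not assessed* where no sample was taken.
5. Base any between-phase laboratory statement on the by-visit tables.

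The cost is SAP wording and a few table columns, all from data already collected. Rates for rare terms will be imprecise: with about 48 men in the oral phase, 48 × 5 = 240 person-weeks, so a single event is 1/240 = 0.42 per 100 person-weeks. Rates also do not correct for visit frequency, which falls from 12 scheduled visits in the 36-week injection phase to 4 in the 48 weeks of follow-up; a footnote should say so.
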